7.4 Patient Numbering

Each patient in the study will be uniquely identified. A Local ID number should be assigned as described in the 7904 Manual of Procedures.

When the patient has signed the informed consent form, the investigator or his/her staff will log onto the electronic data capture system and provide the requested identifying information including the Local ID number for the patient. Participants will maintain the same Local ID for both the Double Blind and Open Label phases, as applicable.

7.5 Randomization Procedure

Subjects will be randomized 1:1 to everolimus or placebo after meeting all eligibility criteria. A designated member of the research team will communicate to the participant that randomization has occurred and sufficient study drug will be dispensed to cover the interval until the next study visit. This is a double-blind study. The study design allows patient unblinding during the double-blind phase only in very precise circumstances (section 7.6.1).

Randomization data are to be kept strictly confidential until the time of unblinding at discontinuation or at the time of final analysis. These data will not be accessible to anyone involved in the conduct of the study with the exception of the unblinded physicians, the Medical Monitor, the Data Safety and Monitoring Committee (DSMC), and the Data Management Coordinating Center (DMCC). The DSMC will review safety data as outlined in section 15. The identity of treatment arms will be concealed by the use of study drugs (everolimus and matching placebo) that are identical in packaging, labeling, schedule of administration and in appearance.

Prior to Baseline (Visit 2), the investigator or his/her designee will log onto the data system to verify that the patient fulfills all eligibility criteria and randomize the patient to a treatment arm. The system will assign a randomization arm, as described in the 7904 Manual of Procedures. The pharmacy will be responsible for dispensing the active drug or placebo based on the procedures outlined in the 7904 Pharmacy Manual of Procedures. The randomization will be stratified by age. Age will be stratified by two levels. Level 1 will be participants aged 5-21 years old, and level 2 will be 22-45 year olds. Permuted block sizes of two and four will be used. At the conclusion of the 6-month double-blind phase, the blind will be broken immediately. Individuals on the active drug will exit the study, and those who were on placebo will be invited to join the open label phase.

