dependent variable predicted by randomization group. We will conduct the analysis with and without conditioning on relevant baseline covariates. The results of these longitudinal analyses can be easily converted to a cross-sectional group effect at each assessment time point to describe the magnitude and significance of group differences. Of particular interest is the group difference at end of treatment (6-month assessment). The mixed effects analyses will be repeated using a model where the baseline scores on each outcome are treated as a baseline covariate to control for (instead of as a part of) the repeated measures. This model can be useful if there is a considerable heterogeneity between before and after treatment processes. We will also analyze the data using conventional ANCOVA treating the end point neurocognitive composite as the dependent variable and controlling for the baseline neurocognitive composite. Further analyses will be conducted using the same analysis models but with transformed data (e.g., log transformation) to check the sensitivity of the results to deviation from outcome normality. Statistical significance of all main effects and interaction terms as well as cross-sectional group differences will be determined using a one-tailed Type 1 error rate of α =.05. The same analysis strategy will be employed for secondary efficacy outcomes and a false discovery rate correction will be implemented to control inflation of Type 1 error.

If the exploratory biosample objectives are pursued, we will explore whether baseline peripheral blood levels of PTEN-associated pathway molecules (PI3K/AKT, mTOR, MAPK protein levels) change with treatment and if changes in peripheral pathway molecules correlate with clinical improvement. To determine whether PTEN-associated pathway molecules change with treatment, we will use a similar mixed effect (growth curve) modeling approach to that described above for Secondary Objective with screening, 3-month, and 6-month pathway measurements as outcome measures. The Time by Randomization Group interaction will test whether the everolimus treatment group shows improvement/normalization of PTEN-pathway molecule levels relative to placebo. This component will be dependent on securing additional funds.

In analyzing the resting state EEG and AEP data we will focus on the following:

- 1. Baseline EEG gamma power
- 2. AEP N1 habituation

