Secondary Objective – Efficacy. For power estimation purposes, the variability in PTEN patients treated with an mTOR inhibitor is expected to be similar to the untreated sample. Preliminary data indicates that the measures which comprise the dominant portion of the neurocognitive composite index (processing speed working memory, and fine motor) are highly sensitive to the brain dysfunction seen in PTEN patients with ASD. The effect sizes are approximately 1 SD or larger. In a comparison between mTOR treated vs. untreated PTEN patients, an effect size of at least 0.65 SD would be of interest and represent clinically- meaningful improvement. For example, an effect size of at least 0.65 SD on cognitive measures would translate to a 10-point standard score improvement in the everolimus-treated group relative to placebo. An improvement of 10 or more points is outside the standard error of measurement for most cognitive measures and is typically considered a reliable change when disordered populations are re-tested.

A sample size of 40 (20 per arm) patients will permit detection of endpoint (6-month follow-up) differences of at least 0.80 SD at the 5% significance level (one-sided alpha = 0.05) with 80% power (1- β). Statistical power will be weaker (1- β =.65) if smaller cross-sectional differences are observed (0.65 SD). However, statistical power is very strong, even for smaller differences (Cohen's d≥.50 equivalent to ≥.50 SD difference) when the full repeated measures nature of the design is considered – baseline, 3-month follow-up, 6-month follow-up. Assuming even modest correlations between repeated measurements of outcome variables (r≥.30), power to detect clinically meaningful differences of .50 SD is very good (1- β =.83; one-sided α =.05). If the primary outcome measure (neurocognitive composite) meets nominal statistical significance in the expected direction (one-tailed p<.05) or a secondary outcome measure meets a more stringent false discovery rate-corrected

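### Randomisation is stratified by age, but no efficacy model commits to the age stratum and no version of the growth model is named as primary; if age predicts change, the unadjusted test is conservative

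*Combined protocol and SAP*

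**What the plan says.** Section 7.5 (Randomization Procedure) sets out a stratified design: "The randomization will be stratified by age". The levels are explicit: "Level 1 will be participants aged 5-21 years old, and level 2 will be 22-45 year olds". Allocation is 1:1, and "Permuted block sizes of two and four will be used".

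Section 17 gives the analyses.

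- **Main efficacy model (objective 2):** a mixed-effects growth curve over baseline, month 3 and month 6, tested through the Time by Randomization Group interaction. The stratum is not mentioned. On covariates it says "We will conduct the analysis with and without conditioning on relevant baseline covariates". No covariates are listed for efficacy, and neither version is declared primary.
- **ANCOVA (objective 2):** month-6 composite adjusted for the baseline composite only.
- **Safety (objective 1):** chi-square or Fisher's exact test, one-tailed at 5%, unstratified. Supporting Cox and logistic models are run with and without covariates, with demographics given as an example.

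Section 17.1 attaches a decision to the efficacy result: a one-tailed p below .05 on the composite makes it a candidate for Phase III.

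**The concern.** When allocation is balanced within strata, differences between strata largely drop out of the treatment estimate. A model without the stratum still counts those differences as residual noise. If the stratum is prognostic for the quantity analysed, the standard error is then too large, the true type I error falls below the nominal 5%, and some power is lost.

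There is also an ambiguity. Two versions of the main model are promised with no rule for which one decides. With 20 per arm they could fall on opposite sides of .05, and section 17.1 acts on that threshold. Power is already modest: section 17.1 states .65 at 0.65 SD, of which it says "an effect size of at least 0.65 SD would be of interest and represent clinically- meaningful improvement".

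**Working it through.** **Inputs from the documents.** 40 patients, 20 per arm; one-sided alpha .05; effects of 0.80 and 0.65 SD; repeated-measures correlation r = .30 (section 17.1); two age strata with blocks of 2 and 4 (section 7.5).

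**Assumptions.** The share of variance explained by the stratum (R²) is not given, so 5%, 10% and 20% are shown. The simulations take 70% of patients as aged 5-21 and no missing data.

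**1. The plan's own figures.** For a two-sample month-6 comparison without baseline or stratum, the noncentrality is d × √(20/2), with 38 df.
- d = 0.80: 0.80 × 3.162 = 2.53, power .799 (stated 80%).
- d = 0.65: 0.65 × 3.162 = 2.06, power .646 (stated .65).

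Both reproduce.

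**2. Effect of omitting a prognostic stratum.** Let R² be the stratum's share of the variance of *the quantity being compared*. With balance within strata, the true SE is √((1−R²)/10) but the unadjusted model reports √(1/10). Under the normal approximation, with δ = d√10:
- true one-sided error = 1 − Φ(1.645/√(1−R²))
- power unadjusted = Φ((δ − 1.645)/√(1−R²))
- power adjusted = Φ(δ/√(1−R²) − 1.645)

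| R² | True error, unadjusted | Power at 0.65 SD, without → with stratum |
|---|---|---|
| 5% | 4.6% | .66 → .68 |
| 10% | 4.1% | .67 → .70 |
| 20% | 3.3% | .68 → .74 |

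A simulation of the block design for a plain month-6 comparison (8,000 runs) agrees in direction and rough size: error 4.8%, 4.4% and 3.6%, with reported standard errors about 2%, 5% and 11% too wide.

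**3. Which R² applies to the planned analyses.** The table holds only for the variance of the quantity actually tested. The main test is on the slope. With three equally spaced visits and complete data, the fitted slope depends only on the change from baseline to month 6.

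- *Constant age effect on level.* It cancels from the change. Simulated error of the slope test (20,000 runs, R² of level 5%, 10%, 20%, r = .30) is .049, .051, .051 without the stratum and the same with it. Nothing is lost.
- *Constant age effect, baseline-adjusted ANCOVA.* The stratum's remaining share is R²(1−r)/(1+r*), where r is the within-stratum correlation and r* = R² + r(1−R²). For r = .30: .05 × .70/1.335 = 2.6%; .10 × .70/1.37 = 5.1%; .20 × .70/1.44 = 9.7%. For r = .70 the shares are 0.9%, 1.7% and 3.4%. Simulated error without the stratum is .046, .047, .044 (r = .30) and .050, .049, .046 (r = .70). The loss is small.
- *Age effect on change (stratum by time).* Here R² is the share of variance in change, so the formula applies to the slope test. Simulated error without the stratum is about .046, .04 and .03-.04. The power column then applies with 0.65 read in SDs of change. An SD of change is √(2(1−r)) SDs of score, so the two units coincide at r = .50.

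**4. No age effect.** At 0.65 SD, power is .646 without the stratum and .645 with it.

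**5. Drop-out.** At the plan's 5% v 40% scenario, one-sided Fisher has power .807 and a stratified exact test .804 with no age effect; with a strong age effect the figures are .815 and .823. The difference is one point or less.

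**The case against.** The strongest reply is that the plan already provides covariate-adjusted versions. The growth model is to be run with conditioning as well as without, and the supporting safety regressions name demographics, which section 7.22 defines to include age. The composite also draws heavily on norm-referenced scores (sections 7.9.3 and 7.9.4), so much of any age effect on level is removed before analysis, and the slope test ignores what remains. Any error is conservative and cannot create a false positive, and section 17 describes the study as exploratory and mainly descriptive.

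Most of this stands, and it limits the size of the point. It would be wrong to infer that the plan excludes age from every analysis; what is missing is a commitment to the stratum and a named deciding version. Nor may the step 2 figures be read as applying to the main model whenever age affects scores: they apply only if age affects change. Two parts of the reply fall short. Age-norming of level does not rule out different change over six months in children and adults. And an unspecified pair of analyses does not settle which one meets the Phase III criterion.

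**Conclusion.** The gap is real and modest. A factor used in randomisation is not carried into the efficacy models by name, and the choice between adjusted and unadjusted versions is left open.

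The size depends on an unknown. If the stratum explains 5%, 10% or 20% of the variance in six-month change, the unadjusted one-sided test runs at about 4.6%, 4% or 3-4% instead of 5%, with roughly 2, 3 or 6 points of power lost at 0.65 SD of change. If age affects only level, the slope test loses nothing and the ANCOVA little; if age has no effect, nothing is lost.

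A reader might infer two stronger things that the documents do not support: that the error bars are certainly too wide, and that the primary safety comparison loses power. The first needs an age effect that the documents do not quantify. The second is contradicted by the drop-out calculation. The point makes inference conservative at worst and invalidates no conclusion.

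**What to change.** In section 17, objective 2:

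1. Include the two-level age stratum and its interaction with time as fixed terms in the growth model. The main effect alone would not help the slope test.
2. Add the stratum to the ANCOVA alongside the baseline composite.
3. Declare the stratum-adjusted growth model the main efficacy analysis, and the one that section 17.1's criterion refers to. Report the unadjusted version as sensitivity.
4. Keep Fisher's exact test as the main drop-out comparison. A stratified exact test is at most a sensitivity analysis, with no material gain in power.

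The cost is a line or two of text and one or two degrees of freedom. It should be settled before unblinded data are analysed.

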Tests that will be conducted during the blinded treatment phase include laboratory tests for safety, physical exams (including a neurological assessment), vital signs, and neuropsychological assessments. If unforeseen circumstances (i.e., unexpected personal reasons) prevent the patient from complying with the established visit schedule, the site can re-schedule the visit (within \pm 14 days of the expected visit date). The reason(s) for any visit or treatment delays will be documented in the CRF for the appropriate visit. All on-site visits (screening,

baseline, month 1, month 3, and month 6) must be completed by the participant, and any missed visits would warrant termination from the study. A summary of the neuropsychological results may be made available at study completion.

At the end of the double-blind phase (or early termination), the treatment code will be broken and the participant will be informed of their assigned treatment arm, using the process outlined in the 7904 Manual of Procedures. Participants who received the active compound will enter the follow-up phase of the study (section 4.5) and will be referred back to their treating physicians. Individuals who were in the placebo group will be invited to enter Phase B, a 6-month open-label extension trial (section 4.4). The inclusion of the open-label phase may increase the acceptability of the project by families and increase their participation in the primary, controlled trial. All participants that received everolimus during the blinded treatment phase will enter the follow-up phase of the trial and will be referred back to their treating physicians. A summary of patient's participation in the study will be provided, if needed.

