4.7 Early Termination

If the participant, legal guardian, or the study physician make the decision to have the participant exit the study early, a follow-up visit must be scheduled 28 days (+/- 14 days) after termination. At this visit, the study physician should review the patient's medical history, concomitant medications, and the DOTES. If the patient exited the trial due to an adverse event, this event should be reviewed and if it is still present the study team must follow-up with the patient/legal guardian for 56 days or until the event has subsided. At the completion of this follow-up visit, the participant may be unblinded and the results may be disclosed to the participant.

5. Recruitment Methods

Recruitment will leverage the observational study, The Natural History of Individuals with Autism and Germline Heterozygous PTEN mutations, and will occur at 3 sites: Cleveland Clinic, Stanford University, and Boston Children's Hospital, with Cleveland Clinic expected to recruit at least 50% of the sample based on extensive experience with PTEN patients at this site. Over the last 5 years, we have recruited and comprehensively evaluated 35+ patients with PTEN ASD only from referrals to Cleveland Clinic and word of mouth. We anticipate that the majority of these individuals would participate in the proposed study.

We will supplement our current recruitment efforts with several complementary strategies. First, [name] (Cleveland Clinic) has developed a registry of > 400 individuals with PTEN mutations that includes > 50 PTEN cases with ASD or evidence of developmental delay. To date, this registry has not been tapped, but it will be used to recruit individuals for the proposed study. [name] lab also regularly screens individuals at risk of PTEN mutations using an online risk calculator and extensive referral network – growing her registry. Second, the two additional sites, Stanford University and Boston Children's Hospital, also have experience with PTEN ASD patients and have an identified population that is interested in participating in this trial. Both of these sites will also leverage their relevant clinics to advertise and recruit for this study. Third, we have obtained support

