7.6 Double-Blind Treatment Assignment Unblinding

Prior to the Month 6 visit or early termination, the site will obtain the unblinded treatment assignment via the procedures described in the 7904 Manual of Procedures. At the conclusion of the double-blind phase or early termination, the blind will be broken immediately. Individuals on the active drug will exit the study, and those who were on placebo will be invited to join the open label phase (section 4.4).

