16.6 Quality Control Method

Standardized data collection and management procedures will be followed to ensure data quality control. Data will be scored, reduced, and managed on an ongoing basis. The PIs will assume responsibility for uniformity across sites and will coordinate on a weekly basis (or more frequently if needed) with the data collection and management team. After data have been collected, it will be entered into the RDCRN DMCC database. As much as possible, data quality is assessed at the data entry point using intelligent on-line data entry via visual basic designed screen forms. Data element constraints, whether independent range and/or format limitations or 'relative' referential integrity limitations, can be enforced by all methods employed for data input. QA reports assess data quality post-data entry. As we note, data quality begins with the design of the data collection forms and procedures and incorporates reasonable checks to minimize transcription and omission errors. Of the more important quality assurance measures are the internal validity checks for reasonableness and consistency.

All variables will be checked for out-of-range values and the marking of missing values.

17. Data Analysis Plan, Statistical Power and Sample Considerations

This is an exploratory study to evaluate the short-term safety and preliminary efficacy of everolimus in patients with a PTEN mutation. The analyses will be predominantly descriptive with the intent of generating plausible hypotheses to be tested in a Phase III confirmatory trial. Efficacy will be assessed using recognized measures of intellectual ability and neurobehavioral processes.

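### Section 7.6 lets the site obtain a patient's code before that patient's Month 6 tests, in conflict with 6.2; blocks of two and four add a smaller leak about later patients

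*Combined protocol and SAP*

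**What the plan says.** **Randomisation (7.5).** "Subjects will be randomized 1:1 to everolimus or placebo after meeting all eligibility criteria". "The randomization will be stratified by age. Age will be stratified by two levels" (5–21 and 22–45 years), and "Permuted block sizes of two and four will be used". Site is not a stratification factor, so as written each block runs across the three sites. Section 5 has "Cleveland Clinic expected to recruit at least 50% of the sample".

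**Release of codes.** Section 7.5: "At the conclusion of the 6-month double-blind phase, the blind will be broken immediately". Section 4.3 says that at the end of the double-blind phase, or at early termination, "the treatment code will be broken and the participant will be informed of their assigned treatment arm". Section 7.6 puts the step earlier: "Prior to the Month 6 visit or early termination, the site will obtain the unblinded treatment assignment". Everolimus patients then leave, and placebo patients are invited into an open-label phase with the same assessments (4.4).

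**Blinding of staff.** Sections 6.2 and 7.16.8 both say the site team is always blind to assignment. Section 7.5 keeps randomisation data from those conducting the study, apart from named unblinded roles, until unblinding at discontinuation or the final analysis. Section 7.9.1 describes the independent evaluators of CGI-S, CGI-I and ADOS-2 as blind. Section 7.9 says only that the neuropsychology testers are very experienced.

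**Early termination (4.7).** The participant may be unblinded once a follow-up visit about 28 days later is complete. Section 7.6 places release before, or immediately at, early termination.

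**The concern.** There are two routes by which staff could know or suspect the arm before outcomes are recorded.

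1. **Direct.** Under 7.6 the site can hold a patient's own code before that patient's Month 6 visit. Section 17 names the 6-month group difference as of particular interest. The same sentence covers early termination. The primary endpoint is drop-out due to side effects, so a reason for leaving could be recorded with the arm already known.
2. **Indirect.** Once earlier patients' codes are out, small balanced blocks carry information about patients still blinded. Known effects of the drug such as stomatitis could sharpen a guess, though the documents give no means of quantifying that.

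At stake are test administration and scoring for the composite, caregiver interviews, and the attribution of side effects and drop-out reasons.

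**Working it through.** **Direct route: the passages side by side**

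| Section | When the code is available | To whom |
|---|---|---|
| 4.3 | End of the double-blind phase, or early termination | Participant |
| 4.7 | After the follow-up visit about 28 days after early termination | Participant |
| 6.2, 7.16.8 | Never | Site team |
| 7.5 | End of that patient's 6 months | Not stated |
| 7.6 | Before the Month 6 visit or early termination | Site |

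These cannot all hold. If 7.6 is followed literally, no guessing is needed.

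**Indirect route: inputs**

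- From the plan: 40 patients, 1:1, two age strata, blocks of 2 and 4, a 2-year enrolment target, 6 months of treatment, one site with at least 50%.
- Assumed: the two block sizes equally likely (1/3 to 2/3 of size 2 also tried); uniform accrual; Month 6 visits in enrolment order; site shares of 50%, 70% and 25%; age split 50:50 (75:25 gave the same result).

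The plan states no figure for predictability, so there is none to reproduce.

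**Overlap.** About 40/24 × 6 = 10 patients are in treatment at any time. With 20 to 30 patients in a stratum, mean spacing is 24/20 = 1.2 to 24/30 = 0.8 months. The chance of a gap above 14 days is exp(−(20/24) × 14/30.4) = 68%, or 56% with 30 patients. Earlier codes are therefore usually out before the next patient's Month 6 visit.

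**All codes and order visible (upper bound).** Guess the arm that is behind, and toss a coin when tied:

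- Block of 2: (1/2 + 1)/2 = 75.0%.
- Block of 4: the third place gives 1/3 × 1 + 2/3 × 1/2 = 2/3, so (1/2 + 2/3 + 2/3 + 1)/4 = 70.8%.
- Equal mix: (1.5 + 2.833)/6 = 72.2%.

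Simulation with the optimal (Bayesian) guess gives 71–72%. About 10% of patients are certain (8–13% over the block mixes) and 53–55% are guessable at 75% or better.

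**Own-site codes only, simulated, blocks of 2 and 4:**

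| Site share | Correct, stratum order unknown | Correct, order known | Certain, order known |
|---|---|---|---|
| 25% | 54% | 56% | about 0.5% |
| 50% | 56–57% | 60% | about 1.5% |
| 70% | 59% | 64% | about 4% |

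**Effect of blocks of 6 and 8**

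- Half-share site, order known: correct guesses fall from 60% to 57%, and patients guessable at 75% or better fall from about 20% to 3%.
- Half-share site, order unknown: 56.5% to 55.7%.
- All codes visible: 72% to 66% correct, and 10% to about 5% certain.

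**Effect of hiding the sizes.** With all codes visible, a guesser who ignores block sizes is right 71% of the time, against 71.5% for one who uses them.

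**The case against.** **The leak from blocks is modest for one site.** Blocks span three sites, so staff at one see only part of each. This stands. A reader might infer from the block sizes that arms are readily predictable, at 72% with one patient in ten certain. That needs one person to hold every site's codes and the enrolment order. Section 16.6 says "The PIs will assume responsibility for uniformity across sites and will coordinate on a weekly basis", but the sentence goes on to make this coordination with the data collection and management team, in a section on data quality. It does not show that codes are shared.

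**Printing the sizes in the protocol is not the cause.** This also stands. Timing of release and block length drive the result.

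**Protections exist.** CGI and ADOS-2 raters are stated to be blind, the composite is built on performance tests, and 7.7.6 requires withdrawals for adverse events to be recorded as such. This lowers the risk but does not cover the composite testers or side-effect attribution. A guess rate is not a bias, and no bias in any estimate has been calculated.

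**The always-blind wording sits beside dose adjustment.** In 6.2 and 7.16.8 it may have been meant for that purpose only. Even so, 7.6 on its own allows the code out before the Month 6 assessments.

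**The Manual of Procedures may restrict access.** It holds the unblinding process and was not available. If it already shields testers, the protocol should say so.

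**Conclusion.** The concern holds, with the weight on the timing and recipients of codes. Section 7.6 lets the site have a patient's own code before the Month 6 visit. That conflicts with 6.2 and 7.16.8, and nothing in the document separates the composite testers from any code.

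Blocks of 2 and 4 are a secondary leak. For staff at one site it is worth about 4 to 14 percentage points above chance across the shares tried (54–64% correct). At a half-share site it is 57–60% correct with about 1.5% of patients certain. These figures rest on the assumed block mix, uniform accrual, site shares and visits in enrolment order. They also take every earlier patient in the stratum as already unblinded, which is somewhat generous to the guesser.

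The documents do not support two stronger conclusions: that assignments are generally predictable, or that results would be biased by a known amount. This should be corrected, with medium confidence, because the manual was not seen.

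**What to change.** 1. **Reconcile 4.3, 6.2, 7.5 and 7.6 (and 4.7 and 7.16.8 with them).** No code goes to the site until that patient's Month 6 ratings, tests and adverse-event attributions are complete and locked. For early leavers, the reason for leaving should be locked as well. Released codes are not given to independent evaluators, neuropsychology testers or other sites while any patient remains blinded. Emergency unblinding under 7.6.1 is unaffected.
2. **For patients not yet randomised, drop block size 2 and use larger varying blocks**, for example 6 and 8.
3. **Optionally, hold the block sizes in a document kept by the data coordinating centre.** On its own this does almost nothing.

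**Cost.** Item 1 is protocol wording plus a same-day sequence at Month 6, since 4.4 expects staff to be ready to dispense open-label drug at that visit. Item 2 needs a new list. Expected imbalance per age stratum rises from about 0.2 to 0.6 patients. Its benefit depends on how many patients are still to be randomised: the trial was activated in June 2017 with a 2-year target, and a page of this version is dated 05Feb20.

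**What remains.** Testers can still infer past arms from who continues into open label, unless different staff test those patients. The leak is reduced, not eliminated.
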